5 GENERAL CONSIDERATIONS FOR DATA ANALYSIS

Statistical analyses will be performed using SAS® (Cary, NC) version 9.3 or above.

All available data will be presented in patient data listings, which will be sorted by site number, unique patient identifier and where appropriate, visit number and visit/assessment date.

5.1 Evaluation of Center Effect

This is a single arm open-label study that will be reported using descriptive stats and a one-sample t-test. Therefore, no adjustments for center effects will be implemented.

5.2 Assessment Windows

No visit windowing required.

5.3 Handling of Dropouts and Missing Data

If the patient withdraws from the study early, but provides an unscheduled or early end-of-Period 1 or end-of-Period 2 VO_{2MAX} assessment then this VO_{2MAX} assessment will be used in the derivation of efficacy endpoints. Only if the unscheduled or early VO_{2MAX} assessment is within ± 7 days of the intended target assessment relative to Day 1, will the derived change in VO_{2MAX} be used in the primary analysis using the Completer Population (see section 7.1, below), but will be used in the supportive analysis, based on the MITT.

Dates will be printed in ISO 8601 date format (YYYY-MM-DD). If only year and month are available, date will be displayed as YYYY-MM. If only year, then just YYYY. Dates that are missing because they are not applicable for the patients are output as “NA”, unless otherwise specified.

Adverse events with missing start dates will be considered as treatment-emergent unless the partial date excludes that possibility, e.g. the adverse event month is prior to the treatment month.

5.4 Other Data Handling Approaches

The programming specification, including the mock-up analysis tables, figures, and data listings, as well as the derived database specification, will be prepared in stand-alone documents. The programming specification document will be finalized prior to the database lock.

Descriptive statistics (n, mean, standard deviation, median, maximum, and minimum) will be used to summarize the continuous data. Unless otherwise stated, descriptive statistics showing the mean or median will be displayed to one more decimal place than the original data; the standard deviation will be displayed to two decimal places more than the original data; minimum and maximum will be displayed to the same number of decimal places as the original data.

Discrete measures will be summarized using counts and percentages. Percentages will be displayed with 1 decimal place and percentages for zero counts will be omitted from the presented results.

P-values will be presented to 4 decimals. When a p-value is less than 0.0001, '<0.0001' will be displayed.

6 ANALYSIS OF DISPOSITION AND PATIENT CHARACTERISTICS

6.1 Disposition and Analysis Populations

The reason given for each screen failure (did not satisfy all inclusion/exclusion criteria, withdrawal by patient, physician decision, adverse event, lost to follow-up, other) will be listed and summarized.

A data listing will be presented to indicate which patients satisfied the criteria for inclusion in the Safety, Modified Intention to Treat, Completer and Pharmacokinetic Populations. The number of patients included in each population will be summarized using counts and percentages, with percentages based on Safety Population as denominator.

Patient disposition will be presented for all patients in the Safety Population. The number and percentage of patients in each of the following disposition categories will be presented, with percentages based on Safety Population as denominator:

- Patients who completed screening (number of patients only)
- Patients who started study treatment
- Patients who completed Period 1 treatment
- Patients who completed Period 2 treatment
- Patients who completed the study as planned to the follow up visit

For patients in the Safety Population who withdraw early from the study treatment or withdrew from the study before the follow up visit, the primary reason for the early withdrawal will be listed and summarized.

6.2 Eligibility Criteria and Protocol Deviations

A list of any inclusion or exclusion criteria failures will be presented in data listings and summarized to show the number and percent of patients failing each criterion for the Safety Population.

Any additional CSR-reportable deviations, drawn from the monitoring reports, will be listed for the Safety Population.

6.3 Demographics and Baseline Characteristics

Demographics characteristics will be presented as data listings and summary statistics using the Safety Population.

Medical history findings reported at Screening will be presented in data listings and summarized to show the number and percent of patients within each Preferred Term within each System Organ Class term for the Safety Population.

6.4 Concomitant Medications

Prior and concomitant medications will be listed by patient for the Safety Population, with an indication of whether the medication was regarded as Prior or Concomitant (see section 3.4.1). Concomitant medications will be summarized by Therapeutic Class and Preferred Term, showing the number and percentage of patients from the Safety Population taking each medication.

6.5 Study Medication

Study medication, in terms of number of tablets dispensed, returned and assumed taken during each study medication accounting period (see section 3.5.1) will be listed for the Safety Population along with the derived estimated total and daily dose.

7 ANALYSIS OF EFFICACY

7.1 Primary Efficacy Analysis

The primary endpoint is the change from Baseline of VO_{2MAX} at the end of Period 2. This will be analyzed using an Analysis of Covariance (ANCOVA) with covariates of baseline VO_{2MAX} and the mean plasma PEX level, with the mean taken from all available Period 2 assessments (> Week 8 to Week 16). The primary analysis population will be the Completer Population and will include an efficacy endpoint from all patients with an assessment within ± 7 days of the planned assessment. The estimated mean change in VO_{2MAX} from Baseline to Period 2 will be presented along with a 95% confidence interval of the change and the p-value. This analysis will be repeated for the percent change from Baseline of VO_{2MAX} at the end of Period 2, including the same covariates.

Descriptive statistics of the Baseline value, VO_{2MAX} at the end of Period 2 and the change and percent change from Baseline to end of Period 2 will be presented for the Completer Population.

The primary analysis and descriptive statistics table will be repeated for the MITT, and will include any imputed change in VO_{2MAX} values for patients who did not complete the study to the end of Period 2 but provided an end of Period 2 VO_{2MAX} assessment (see section 3.1.1).

Example SAS code is shown below:

```
proc mixed data=dataP2;
  class Period;
  model CHG=BASE PEXALL Period/ solution cl;
  lsmeans Period/ cl;
run;
```

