8.4.3 Efficacy Analyses

All CPEX tests will be assessed by the centralized CPEX assessor for compliance with prospectively defined CPEX test-protocol criteria.

A two-sided, one-sample t-test is planned for the comparison of VO₂MAX at the end of Period 2 compared to baseline. The secondary and exploratory efficacy endpoints of the study will be examined by appropriate statistical methods as described in the statistical analysis plan.

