8.4.7 Ongoing Data Review and Analyses

8.4.7.1 Study Monitoring Team

All available data will be presented in listings approximately every 2 months (until the study is completed) following 25% enrollment in the study with an emphasis on observed outcomes related to patient safety and tolerance (*i.e.*, AEs, ADEs, vital signs measurements, ECGs, laboratory assessments, and concomitant medications). These listings will be reviewed by the Study Monitoring Team to determine whether the dosing regimen should be altered during the course of the study or whether any other protocol modifications or actions should be instituted to ensure the safety of the patients.

8.4.7.2 CPEX Analysis Following Completion of Period 1

A snapshot of the database will be taken for the CPEX data (listings and summary statistics) when all patients have completed Week 8. A two-sided, one-sample t-test will be performed for the comparison of VO₂MAX at the end of Period 1 compared to baseline.

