7.2 Secondary Efficacy Analyses

7.2.1 *Difference between Period 2 and Period 1 Change from Baseline in VO₂MAX*

The first secondary efficacy endpoint is the change from Baseline of VO₂MAX at the end of Period 1 compared to the change from Baseline at the end of Period 2. This will be analyzed using an ANCOVA with covariates of baseline VO₂MAX and the Period-mean plasma PEX level for the Completer Population. The estimated mean change in VO₂MAX from Baseline to Period 1 and to Period 2 and the difference between Period 1 and Period 2 will be presented along with a 95% confidence interval and the p-value. This analysis will be repeated for the MITT, and will include any imputed change in VO₂MAX as in the primary analysis.

Example SAS code is shown below:

```
proc mixed data=dataP1P2;  
  class Period;  
  model CHG=BASE PEXP1P2 Period/ solution cl;  
  lsmeans Period/ cl diffs;  
  estimate "Period 2 vs. Period 1" Period -1 1/ cl;  
run;
```

7.2.2 *Change from Baseline in VO₂MAX at the end of Period 1*

The second secondary efficacy endpoint is the change from Baseline of VO₂MAX at the end of Period 1. Similar to the primary efficacy endpoint, this will be analyzed using an ANCOVA with covariates of baseline VO₂MAX and the Period 1 mean plasma PEX level for the Completer Population. This will be repeated for the MITT, including any imputed change in VO₂MAX values for patients who did not complete the study to the end of Period 1. Descriptive statistics of the Baseline value, VO₂MAX at the end of Period 1 and the change from Baseline to end of Period 1 will be presented for the Completer Population and the MITT Population.

7.2.3 *Change from Baseline in 6MWT at the end of Period 2*

The change from Baseline in the 6MWT at the end of Period 2 will be analyzed using an ANCOVA with covariates of baseline VO₂MAX and the Period 2 mean plasma PEX level. This will be presented for the Completer Population and repeated for the MITT including any imputed change from Baseline values for patients who did not complete the study to the end of Period 2.

7.2.4 *Difference between Period 2 and Period 1 Change from Baseline in 6MWT*

The change from Baseline in the 6MWT at the end of Period 1 compared to the change from Baseline at the end of Period 2 will be analyzed using an ANCOVA with covariates of baseline VO₂MAX and the Period-mean plasma PEX level Completer Population and repeated for the MITT.

7.2.5 *Change from Baseline in 6MWT at the end of Period 1*

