11 SAMPLE SIZE AND POWER CONSIDERATIONS

The sample size was based on a two-sided, one-sample t-test of the change from Baseline for the end of Period 2 with the following assumptions:

- Mean change from Baseline for Period 1 is 1.2mL O₂/kg/min
- Mean change from Baseline for Period 2 is 2.0mL O₂/kg/min
- Standard deviation of change from Baseline is 2.5mL O₂/kg/min for both periods
- Significance level (alpha) of 0.05

With these assumptions, a power of > 95% is anticipated for the primary outcome, and 72% for the first secondary outcome is expected for a sample size of 30 patients.

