12 CHANGES FROM PROTOCOL-SPECIFIED STATISTICAL ANALYSES

1. Added Modified Intention to Treat Population as a sensitivity analysis population for efficacy analyses.
2. Added inclusion of early withdrawal efficacy assessments in efficacy analyses that use the MITT Population.
3. The protocol specified that each analysis would be performed using a t-test. During preparation of the statistical analysis plan, it was decided to change this to analysis of covariance (ANCOVA). The intention was to allow covariate adjustment for a Baseline value, to adjust for baseline severity, and in some analyses the plasma PEX level, to adjust for some measure of study medication intake level.

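### The one-arm, one-period ANCOVA for VO2MAX leaves the mean change unaltered but gives a 95% CI and p-value that are too optimistic for the patient population if baseline or PEX level predicts change

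*SAP*

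**What the plan says.** Protocol 8.4.3 on the primary endpoint: "A two-sided, one-sample t-test is planned for the comparison of" VO2MAX at the end of Period 2 with baseline. Protocol 8.4.7.2 sets the same test for Period 1: "A two-sided, one-sample t-test will be performed for the comparison of" VO2MAX at the end of Period 1 with baseline. SAP 10 repeats that Period 1 test.

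SAP 7.1 instead fits an ANCOVA to the Period 2 change, with baseline VO2MAX and the Period 2 mean PEX level as covariates. The example code has a single Period level and takes its LS mean. The estimated mean change "will be presented along with a 95% confidence interval of the change and the p-value". SAP 7.2.2 covers Period 1: "Similar to the primary efficacy endpoint, this will be analyzed using an ANCOVA with covariates of baseline" VO2MAX and Period 1 mean PEX level.

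SAP 12 item 3 discloses the switch and gives adjustment for baseline severity and drug level as the reason. Two other places still rest on the t-test:
- SAP 5.1: "This is a single arm open-label study that will be reported using descriptive stats and a one-sample t-test".
- SAP 11: "The sample size was based on a two-sided, one-sample t-test of the change from Baseline for the end of Period 2".

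**The concern.** In a randomised comparison, adjusting for a prognostic covariate removes chance imbalance between arms and sharpens the treatment contrast. Here there is no second arm, and each of these analyses uses one period, so there is no imbalance to remove and adjustment cannot improve the estimate of the mean change. What it does change is the standard error: variation in change explained by baseline or PEX level is taken out, as though those covariate values were fixed by design. They are in fact part of the sample.

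The primary objective concerns patients with HCM, and readers will take the primary CI as a statement about them. For that target the printed interval may be too short and the p-value too small, in an uncontrolled study where this mean change is the main efficacy result. Period 1 VO2MAX could also receive two different p-values, one from the t-test in SAP 10 and one from the ANCOVA in SAP 7.2.2.

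**Working it through.** **Inputs.** From protocol 8.2 and SAP 11: n = 30, SD of change 2.5 mL O2/kg/min, two-sided alpha 0.05, mean change 1.2 (Period 1) and 2.0 (Period 2). The share of variance in change explained by the covariates (R2) is not in the documents; it is assumed and shown over a range starting at zero.

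**1. The plan's own power.** Exact one-sample t-test, 29 df, critical value 2.0452, noncentrality = change / 2.5 × √30:
- change 2.0: noncentrality 4.38, power 98.8% (stated: above 95%)
- change 1.2: noncentrality 2.63, power 71.9% (stated: 72%)

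Both reproduce. The protocol synopsis ties the 72% to a change of 1.2. Protocol 8.2 and SAP 11 attach it to the first secondary outcome, which SAP 7.2.1 defines as the Period 2 versus Period 1 comparison. It is used here only as the power for a one-sample change of 1.2.

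**2. What the ANCOVA reports.** A least-squares fit with an intercept passes through the sample means. Evaluated at the covariate means, as LSMEANS does by default, the fitted value is the raw mean change. Its SE is residual SD / √n on n − 3 = 27 df. A fitted example with 30 simulated patients confirmed this: LS mean and raw mean were both 1.983, with SE 0.334 from the ANCOVA and 0.358 from the t-test.

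**3. True size and power.** The mean change has sampling variance 2.5²/30, whereas the ANCOVA SE estimates 2.5² × (1 − R2)/30. With normal data:
- true size = 2 × P(T27 > 2.0518 × √(1 − R2))
- power: same threshold, noncentral t on 27 df
- CI half-width ≈ 2.0518 × 2.5 × √(1 − R2) / √30, against 2.0452 × 2.5 / √30 = 0.93 for the t-test

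| R2 | True size | Half-width | Power at 1.2 (t-test 71.9%) | Power at 2.0 (t-test 98.8%) |
|---|---|---|---|---|
| 0 | 5.0% | 0.94 | 71.7% (−0.2) | 98.8% (0.0) |
| 0.0625 | 5.7% | 0.91 | 73.8% (+1.9) | 99.0% (+0.2) |
| 0.127 | 6.6% | 0.87 | 76.0% (+4.1) | 99.2% (+0.3) |
| 0.2125 | 8.0% | 0.83 | 78.9% (+6.9) | 99.4% (+0.5) |
| 0.32 | 10.2% | 0.77 | 82.4% (+10.4) | 99.6% (+0.7) |

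Differences in brackets are percentage points, taken before rounding. The apparent gain in power comes with the excess type I error, so it is not a real gain.

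**4. Simulation.** With 400,000 trials per setting, ANCOVA rejection at zero change was 4.95, 5.73, 6.57, 7.95 and 10.27%; the t-test stayed at 4.95–5.01%. At a change of 1.2, the share of trials significant by ANCOVA only was 0.8, 2.4, 4.4, 7.0 and 10.4%; by t-test only, 1.0, 0.5, 0.2, 0.1 and 0.0%. At 2.0, ANCOVA-only was at most 0.72%. With PEX level uniform within a band and n of 24, 30 or 33, size was 4.9–5.0% at R2 0, 5.7% at 0.0625, 6.5–6.7% at 0.127 and 7.7–8.0% at 0.2125.

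**5. When the ANCOVA interval is the shorter one.** On average, once population R2 exceeds 1 − (2.0452/2.0518)² = 0.006. In a given trial, once sample R2 exceeds 1 − (2.0452/2.0518)² × 27/29 = 0.075. That happens in 35, 62, 80, 93 and 98% of trials at the five R2 values.

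**6. Which R2 is plausible.** Change contains minus baseline. With equal variances at both visits and test-retest correlation r, baseline alone gives R2 = (1 − r)/2 = (2.5 / (2 × SD))², where SD is the cross-sectional SD of VO2MAX. That SD is also not in the documents. Assumed values of 5 and 3.5 give 0.0625 and 0.128; an SD of 2.7 would give 0.21. At the SDs of 3.5 to 5, the two largest R2 values need PEX level to predict change as well, which titration into 300–500 ng/mL makes less likely.

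**The case against.** **The effect on the primary endpoint is small.** This stands. At a change of 2.0 the net shift is at most 0.7 points, and half-width falls from 0.93 to 0.87–0.91 if R2 is 0.06 to 0.13. It limits the weight of the point without making the interval right.

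**The mitigations are already there.** In part. SAP 5.4 says "Descriptive statistics (n, mean, standard deviation, median, maximum, and minimum) will be used to summarize the continuous data", so a reader could rebuild the t-test for Period 2, and SAP 10 runs the t-test on the Period 1 snapshot, though possibly on a different patient set from the Completer Population. The CI and p-value presented for the primary endpoint remain those of the ANCOVA.

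**ANCOVA is valid conditionally and was disclosed.** Both are true. The interval is correct for the mean at the observed covariate values. SAP 7.1 does not label it so, and the reason given in SAP 12, adjustment for severity and drug level, does not alter the estimate in a single arm.

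**Lighter remedies exist.** Adding the covariate-mean variance to the SE is sound, but it nearly rebuilds the t-test SE. A note that the CI is conditional leaves the headline p-value on the wrong target. An extra t-test row leaves open which result is primary.

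**The R2 values are assumed.** They are, and so is the cross-sectional SD. The direction does not depend on them; at R2 = 0 there is no inflation, and the ANCOVA interval is narrower in only 35% of trials.

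**Conclusion.** The concern holds. Under SAP 7.1 and 7.2.2 the estimate is the raw mean change, and its CI and p-value are too optimistic for the HCM patient population whenever baseline VO2MAX or PEX level predicts change. If neither does, the test keeps its 5% size and nothing is gained. Under the assumed baseline-only R2 of 0.06 to 0.13, true size is 5.7% to 6.6%. The primary conclusion would rarely change at the planned effect; Period 1, or a Period 2 effect below plan, is more exposed.

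This assumes complete covariates, default LSMEANS, approximately normal data, and n = 30 with SD 2.5. No size can be given for the 6MWT, and the two-period comparisons in SAP 7.2.1 and 7.2.4 are outside this point. The change should be made; confidence is medium because R2 is unknown.

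**What to change.** In SAP 7.1 and 7.2.2, make the two-sided one-sample t-test at alpha 0.05, with its t-based 95% CI, the headline analysis of the VO2MAX change at the end of Period 2 and Period 1, as in protocol 8.4.3 and 8.4.7.2. Keep the ANCOVA as a supportive model that reports the slopes of change on baseline VO2MAX and on PEX level with 95% CIs, and revise SAP 12 item 3 to match. SAP 5.1, out of date against the present 7.1, then becomes correct; SAP 10 and 11 need no change. In SAP 7.2.3 and 7.2.5, use the same t-test if a CI or p-value for the mean 6MWT change is reported.

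The cost is SAP and table-shell wording before database lock, which SAP 1 allows; no new data are needed. The primary CI may be slightly wider: half-width 0.93 against about 0.87–0.91 under the assumed baseline-only R2.

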4 ANALYSIS POPULATIONS

4.1.1 *Safety Population*

The Safety Population will include all patients who receive study drug.

4.1.2 *Modified Intention to Treat Population*

The Modified Intention to Treat Population (MITT) will include all patients who receive study drug and have at least one post-Baseline efficacy assessment.

4.1.3 *Completer Population*

The Completer Population will include all patients who receive study drug and complete all study procedures at Baseline, end of Period 1 and end of Period 2 and have their Period 2 CPEX assessment within 7 days of the target day of 113.

4.1.4 *Pharmacokinetic Population*

The Pharmacokinetic Population will include all patients who receive study drug and had at least one plasma sample collected.

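### The MITT repeat of the primary analysis has no row for patients with a Week 8 CPEX but no Period 2 CPEX, so it cannot address bias from patients who leave untested in Period 2

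*SAP*

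**What the plan says.** The primary analysis uses the Completer Population (SAP 4.1.3 and 7.1): all procedures at Baseline, end of Period 1 and end of Period 2, with the Period 2 CPEX within 7 days of Day 113. SAP section 12, item 1, describes the one addition meant to test this: "Added Modified Intention to Treat Population as a sensitivity analysis population for efficacy analyses". MITT members receive study drug and "have at least one post-Baseline efficacy assessment" (SAP 4.1.2), so a Week 8 CPEX or 6MWT is enough.

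In SAP 7.1 the MITT repeat includes *imputed* changes, but only "values for patients who did not complete the study to the end of Period 2 but provided an end of Period 2" VO2MAX. The example code begins "proc mixed data=dataP2". SAP 3.1.1 and 5.3 show that the imputed value is an observed unscheduled or early CPEX. No rule covers a patient who has none.

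Protocol 6.11 asks sites to attempt a CPEX at withdrawal but cannot guarantee it. Protocol 8.5 rules out replacement. Protocol 8.3 also promises a repeat of the efficacy analysis on the Safety Population. SAP section 7 does not carry that repeat forward, SAP section 12 does not list its removal, and it had no missing-data rule either.

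**The concern.** A completer analysis is open to question mainly because of the patients who do not complete. A sensitivity analysis should bring them back, or show how much they could matter. Here a patient who stops in Period 2 without another exercise test is absent from both the primary analysis and its repeat, although the Week 8 change is on file. Protocol 4.6 adds a route out that is tied to the endpoint itself: discontinuation is mandatory for patients unable or unwilling to repeat a CPEX that failed the acceptance criteria.

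If such patients respond less well than those who stay, both analyses overstate the Period 2 mean in the same direction, and agreement between them says nothing about it. With one arm, no comparator offsets the bias. The estimate matters because the study is meant to settle the dosing regimen for a Phase 3 trial (Protocol 2.8, SAP 2.2).

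**Working it through.** **Inputs from the documents.** SAP 11: "The sample size was based on a two-sided, one-sample t-test"; "Significance level (alpha) of 0.05"; "Mean change from Baseline for Period 2 is 2.0mL"; "Mean change from Baseline for Period 1 is 1.2mL" (both means in mL O2/kg/min); SD of change 2.5 in both periods. Protocol synopsis: about 33 enrolled and 30 expected to complete, so 3/33 = 9.1% do not.

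**Assumptions not in the documents.** Correlation rho of 0.5 to 0.7 between a patient's Week 8 and Week 16 changes; strength g of the link between leaving and poor response (0, 0.5 or 1.0); every leaver goes after Week 8 with no Period 2 CPEX; the six-leaver case.

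**The plan's own figure.** One-sample t-test, n = 30, df = 29, noncentrality 2.0/2.5 × √30 = 4.38: power 98.8%, in line with the stated > 95%. A mean of 1.2 tested against zero gives 71.9%, against the stated 72%. Enrolment: 30/(1 − 3/33) = 33.

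**Who has a row in each analysis.**

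| Patient | Completer primary | MITT repeat |
|---|---|---|
| All procedures, Period 2 CPEX in window | yes | yes |
| Period 2 CPEX in window, another required procedure missed | no | yes |
| Early or unscheduled Period 2 CPEX outside ±7 days | no | yes |
| Week 8 CPEX, no Period 2 CPEX | no | in the population, no row |
| No post-Baseline efficacy test | no | not in the population |

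The model also needs a Period 2 mean PEX level, which is undefined for a patient with no Period 2 sample.

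**Size of the bias, on raw means.** Suppose the k of N patients with the highest leaving score drop out. Then

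bias = k/(N − k) × c × SD × m,

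where m is the expected mean of the k largest of N standard normal scores (1.72 for 3 of 33, by numerical integration) and c is the correlation of the leaving score with poor Period 2 change. So c = g × rho if leaving depends on Period 1 change, and c = g if it depends on Period 2 change.

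- Period 1 mechanism, g = 0.5: 0.1 × 0.5 × 0.5 × 2.5 × 1.72 = 0.11 at rho 0.5; 0.1 × 0.5 × 0.7 × 2.5 × 1.72 = 0.15 at rho 0.7.
- Period 1 mechanism, g = 1.0: double these, 0.22 and 0.30.
- Period 2 mechanism, g = 0.5: 0.1 × 0.5 × 2.5 × 1.72 = 0.22.
- g = 0: zero.

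**With a joint model.** For this missing-data pattern the estimate is the completer Period 2 mean plus slope × (all-patient minus completer Period 1 mean). Under the Period 1 mechanism the correction is complete. Under the Period 2 mechanism about (1 − rho²) of the bias remains: 0.75 × 0.215 = 0.16 at rho 0.5, and 0.51 × 0.215 = 0.11 at rho 0.7.

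**Simulation check.** Period 1 mechanism, g = 0.5: 20,000 trials gave 0.105 and 0.157 as planned; 200,000 trials gave 0.106 and 0.152. The joint estimate was within 0.01 of zero bias. Period 2 mechanism, g = 0.5, 200,000 trials: 0.215 and 0.214 as planned, against 0.164 and 0.112 jointly. The SD of the estimate is 0.44 to 0.46 either way.

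**Six leavers.** Period 1 mechanism: about 0.20 to 0.27 (g = 0.5) and 0.39 to 0.55 (g = 1.0) as planned. Period 2 mechanism, g = 1.0: about 0.78 as planned, 0.49 to 0.65 jointly.

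**Does it threaten significance?** With completer mean c₀, n completers and missing-patient mean μ, all 33 patients have mean (n·c₀ + (33 − n)μ)/33 and variance [31 × 6.25 + n(33 − n)/33 × (c₀ − μ)²]/32. For 3 missing and c₀ = 2.0, t falls to its critical value of 2.04 at μ = −6.4: mean 1.23, SD 3.48, standard error 0.61. With no change at all in the 3 missing, the overall mean is 60/33 = 1.82 and power is 97.9%. Other tipping points: −2.9 (6 missing) and −1.5 (9 missing). If the completer mean is only 1.2: −1.8, −0.4 and +0.07 for 3, 6 and 9 missing.

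**The case against.** A fair defence has four parts.

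1. The repeat does deal with some dropout. Early and out-of-window tests enter it, as do patients who missed another procedure, and SAP section 12, item 2, gives early-withdrawal assessments as the stated purpose. A reader might infer that the repeat merely duplicates the Completer analysis, or that the SAP will present agreement as proof of robustness to dropout. The documents support neither.
2. A joint model is unbiased by construction when leaving depends on the observed Week 8 change. For patients too unwell in Period 2 to be tested, it keeps much of the bias: roughly half to four-fifths across the scenarios run. It does nothing for patients who leave before Week 8 without a post-Baseline CPEX, such as Day 8 withdrawals. This stands, and it is why the fix needs a tipping-point analysis as well.
3. At the planned dropout the moderate bias is small: 0.11 to 0.15 is a quarter to a third of the standard error (2.5/√30 = 0.46). This stands too.
4. SAP 7.2.1 already fits both periods in the MITT, and SAP 5.4, 6.1 and 7.1 already yield most of the counts. But the 7.2.1 code has no repeated-measures structure, so a patient's Week 8 change does not inform the Period 2 mean through within-patient correlation.

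The illustration uses raw means, whereas the plan fits an ANCOVA. The missing rows are the same, but the exact figures would differ.

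**Conclusion.** The point holds for one group: MITT patients with a Week 8 CPEX and no Period 2 CPEX. They have no row, no imputation rule stands behind the word *imputed*, and so the SAP's only efficacy sensitivity population cannot address bias from their leaving.

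With 3 such leavers the Period 2 mean could be too high by about 0.11 to 0.15 under moderate dependence on Period 1 change, 0.22 to 0.30 under complete dependence, and about 0.22 under moderate dependence on Period 2 change. It is unbiased if leaving is unrelated to response. These are illustrations under the assumptions listed, not bounds.

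A reader might infer that the primary result itself is in doubt. At 3 of 33 non-completers and the assumed effect, it is not: the missing patients would need a mean change of −6.4. The effect is on the estimate. It grows with more dropout or a smaller true effect, and then the conclusion could rest on patients whom the planned repeat cannot show. The change is worth making, but it is not critical.

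**What to change.** In SAP 7.1, fit the MITT sensitivity analysis to the Week 8 and Week 16 changes of all MITT patients. Use baseline VO2MAX and Period as fixed effects, `repeated Period / subject=patient type=un`, and no PEX covariate, and report the Period 2 mean with its 95% CI. Leave PEX out because the Period 2 average does not exist for a patient with no Period 2 level.

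Fit the same model to the Completer Population, so that any difference reflects who is included and not which model is used.

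Add a tipping-point (delta) analysis covering all dosed patients without a Period 2 CPEX, including those with no post-Baseline test, and report their number. State plainly that *imputed* means an observed early or unscheduled test. Do the same for 6MWT in SAP 7.2.3. Reconcile the MITT repeat with the Safety Population repeat in Protocol 8.3, or list the change in SAP section 12.

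The cost is a few lines of SAP text and code, which SAP section 1 allows before database lock, and slightly more analysis work. The primary Completer analysis is untouched and precision is essentially unchanged. The joint model assumes that dropout depends on observed values; the tipping-point analysis probes that assumption.
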